6.1.3 RAD001 Dose Level Modification/Interruption Guidelines in Case of Suspected Toxicity

Dose adjustments are permitted in those patients who are unable to tolerate the protocol-specified dosing schedule. If administration of RAD001 must be interrupted because of unacceptable toxicity, drug dosing will be interrupted or modified according to rules described in [Table 2](#), [Table 3](#), and [Table 4](#).

If the toxicity is tolerable to the patient, the initial dose should be maintained. If the toxicity is intolerable to the patient, RAD001 treatment is to be interrupted until recovery to grade ≤ 1 , then reintroduced at the initial dose or a lower dose level, depending on toxicity type and grade (see [Table 3](#)). All interruptions or dose modifications must be recorded on the Dosage Administration Record CRF.

Table 2 RAD001 Dose Level Modification Guidelines

Dose Level	Dose Schedule
0	10 mg daily
1	5 mg daily
2	5 mg every other day

Table 3 provides the procedure to be followed for dose modification and re-initiation of RAD001 in the event of toxicities suspected to be related to the study drug.

Table 3 Criteria for Dose Modification in Case of Suspected RAD001 Toxicity

Toxicity	Actions
Non-hematological toxicity	
Grade 1	No dose modification.
Grade 2 (except pneumonitis):	If the toxicity is tolerable to the patient, maintain the same dose. If toxicity is intolerable to the patient, interrupt RAD001 until recovery to grade ≤ 1 , then re-introduce RAD001 at the same dose. If the event returns to grade 2, interrupt RAD001 until recovery to grade ≤ 1 , then re-introduce at the lower dose level.
Grade 3 (except hyperlipidemia):	Interrupt RAD001 until recovery to grade ≤ 1 , then re-introduce at the lower dose level. For pneumonitis, consider the use of a short course of corticosteroids.
Grade 3 hyperlipidemia (hypercholesterolemia and/or hypertriglyceridemia):	Should be managed using standard medical therapies.
Grade 4:	Discontinue RAD001.
Reactivation of HBV or HCV	Please refer to Tables 6 and 7 .
Hematological toxicity	
Grade 1	No dose modification.
Grade 2 thrombocytopenia (platelets $<75 \times 10^9/L$, $\geq 50 \times 10^9/L$):	Interrupt RAD001 until recovery to grade ≤ 1 (platelets $\geq 75 \times 10^9/L$), then re-introduce RAD001 at the initial dose. If thrombocytopenia returns to grade 2, interrupt RAD001 until recovery to grade ≤ 1 , then re-introduce at the lower dose level.

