Grade 3 thrombocytopenia (platelets $<50 \times 10^9/L$, $\geq 25 \times 10^9/L$):	Interrupt RAD001 until recovery to grade ≤ 1 (platelets $\geq 75 \times 10^9/L$), then resume RAD001 at 1 dose level lower. If grade 3 thrombocytopenia recurs, discontinue RAD001.
Grade 4 thrombocytopenia (platelets $<25 \times 10^9/L$):	Discontinue RAD001.
Grade 3 neutropenia (neutrophils $<1 \times 10^9/L$, $\geq 0.5 \times 10^9/L$):	Interrupt RAD001 until recovery to grade ≤ 1 (neutrophils $\geq 1.5 \times 10^9/L$), then resume RAD001 at initial dose. If absolute neutrophil count (ANC) returns to grade 3, hold RAD001 until recovery to grade 1 (ANC $\geq 0.5 \times 10^9/L$), then resume RAD001 at the lower dose level. Discontinue patient from study therapy for a third episode of grade 3 neutropenia.
Grade 4 neutropenia (neutrophils $<0.5 \times 10^9/L$):	Interrupt RAD001 until recovery to grade ≤ 1 (neutrophils $\geq 1.5 \times 10^9/L$), then resume RAD001 at the lower dose level. If grade 3 or grade 4 neutropenia occurs despite this dose reduction, discontinue RAD001.
Grade 3 febrile neutropenia (not life-threatening):	Interrupt RAD001 until resolution of fever and neutropenia to grade ≤ 1 . Hold further RAD001 until the ANC $\geq 1500/mm^3$ and fever has resolved. Resume RAD001 at the lower dose level. If febrile neutropenia recurs, discontinue RAD001.
Grade 4 febrile neutropenia (life-threatening):	Discontinue RAD001.
Any hematological or non-hematological toxicity	Discontinue RAD001.

requiring interruption for ≥ 3 weeks:

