6.1.4 Monitoring of RAD001 Suspected Toxicities

Patients whose treatment is interrupted or permanently discontinued due to an AE or abnormal laboratory value suspected to be related to RAD001 must be followed at least weekly until the AE or abnormal laboratory value resolves or returns to grade 1.

If a patient requires a dose delay of >21 days from the intended day of the next scheduled dose, then the patient must be discontinued from the study.

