6.1.4.4 Management of hepatitis reactivation

Monitoring and Prophylactic Treatment for Hepatitis B Reactivation

[Table 5](#) provides details of monitoring and prophylactic therapy according to the screening results of viral load and serologic markers testing.

Test	Result	Result	Result	Result	Result
HBV-DNA	+	+ or -	-	-	-
HBsAg	+ or -	+	-	-	-
HBsAb	+ or -	+ or -	+ and no prior HBV vaccination	+ or -	or + with prior HBV vaccination

HBcAb	+ or -	+ or -	+ or -	+	-
Recommendation	Prophylactic antiviral treatment should be started 1-2 weeks prior to first dose of study drug. Monitor HBV-DNA every 6 weeks		No prophylaxis Monitor HBV-DNA every 3 weeks		No specific action

Table 5 Action to be taken based on Screening Hepatitis B Results

Antiviral prophylaxis therapy should continue for at least 4 weeks after last dose of study drug. For HBV reactivation definition and management guidelines, see [Table 6](#).

Table 6 Guidelines for the management of Hepatitis B reactivation

HBV reactivation (with or without clinical signs and symptoms)*	

For patients with baseline results: Positive HBV-DNA OR positive HBsAg
 
-----
 
reactivation is defined as: [Increase of 1 log in HBV-DNA relative to baseline HBV-DNA value OR new appearance of measurable HBV-DNA] AND ALT elevation x 5 ULN
	
Treat: Start a second antiviral AND Interrupt study drug administration until resolution:
 
 • ≤ grade 1 ALT (or baseline ALT, if > grade 1) and • ≤ baseline HBV-DNA levels 
If resolution occurs within ≤ 28 days, study drug should be re-started at one dose lower, if available (see Table 6-1 for dose levels available). If the patient is already receiving the lowest dose of study drug according to the protocol, the patient should restart at the same dose after resolution. Both antiviral therapies should continue at least 4 weeks after last dose of study drug.
 
If resolution occurs > 28 days, patients should discontinue study drug but continue both antiviral therapies at least 4 weeks after last dose of study drug.

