
For patients with baseline results: Negative HBV-DNA and HBsAg
 
AND [Positive HBsAb (with no prior history of vaccination against HBV), OR positive HBcAb]
 
-----
 
reactivation is defined as: New appearance of measurable HBV-DNA
	
Treat : Start first antiviral medication AND Interrupt study drug administration until resolution:
 
 • ≤ baseline HBV-DNA levels 
If resolution occurs within ≤ 28 days, study drug should be re-started at one dose lower, if available (see Table 6-1 for dose levels available). If the patient is already receiving the lowest dose of study drug according to the protocol, the patient should restart at the same dose after resolution. Antiviral therapy should continue at least 4 weeks after last dose of study drug.
 
If resolution occurs > 28 days Patients should discontinue study drug but continue antiviral therapy at least 4 weeks after last dose of study drug.

* All reactivations of HBV are to be recorded as grade 3 (CTCAE Version 3.0 – Metabolic Laboratory/Other: Viral Reactivation), unless considered life threatening by the investigator, in which case they should be recorded as grade 4. Date of viral reactivation is the date on which DNA (and ALT) criteria were met (e.g., for a patient who was HBV-DNA positive on 01-JAN-10 and whose ALT reached ≥ 5 × ULN on 01-APR-10, the date of viral reactivation is 01-APR-10).
	

Monitoring for Hepatitis C Reactivation

The following two categories of patients should be monitored every 6 weeks for HCV reactivation:

- Patients with detectable HCV RNA-PCR test at baseline
- Patients known to have a history of HCV infection, despite a negative viral load test at baseline (including those that were treated and are considered „cured“)

For definitions of HBV or HCV reactivation and actions to be taken in the event of reactivation, please refer to [Table 7](#).

Table 6 Guidelines for the management of Hepatitis C reactivation

HCV reactivation*	
For patients with baseline results: Detectable HCV-RNA reactivation is defined as: ALT elevation x 5 ULN	Discontinue study drug
For patients with baseline results: Knowledge of past hepatitis C infection with no detectable HCV-RNA reactivation is defined as: New appearance of detectable HCV-RNA	Discontinue study drug

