6.6.5 Interruption or Discontinuation of Study Drug

The term “interruption” refers to a patient stopping all study drug during the course of the study, but then re-starting it at a later time in the study. If treatment has to be interrupted for more than 14 days for any reason other than toxicities suspected to be related to RAD001, the patient will be discontinued from the study. If treatment has to be interrupted for more than 21 days due to suspected study drug-related toxicity, the patient will be discontinued from the study.

Tumor evaluations will continue until the start of new anticancer therapies. The term “discontinuation” refers to a patient’s premature withdrawal from the study treatment. In accordance with the current revision of the Declaration of Helsinki and current US Food and Drug law, a patient has the right to withdraw from the study at any time for any reason without prejudice to his/her future medical care by the physician or at the institution.

The reason for discontinuation from treatment will be recorded on the appropriate CRF page. The patient may discontinue participation in the study for any of the following reasons:

1. Adverse event(s);
2. Abnormal laboratory value(s);
3. Abnormal test procedure result(s);
4. Disease progression;
5. Protocol violation;

6. Patient withdrew consent;
7. Lost to follow-up;
8. Administrative problems;
9. Death.

If a patient has discontinued the study due to an unacceptable adverse drug reaction or an abnormal laboratory value, he/she should not have withdrawal of consent recorded as the reason for discontinuation. Instead, the reason for discontinuation must be recorded as due to adverse drug reaction or an abnormal laboratory value.

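### Table 6 restarts study drug when HBV reactivation resolves within 28 days, but Sections 6.1.4, 6.6.3.1 and 6.6.5 discontinue the patient after more than 21 days (14 if not drug-related), with no hepatitis exception

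*Protocol*

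**What the plan says.** **The hepatitis rule.** Table 6 (Hepatitis B) in protocol Section 6.1.4.4 covers two baseline groups: patients positive for HBV-DNA or HBsAg, and patients negative for both who carry antibody markers. In both, reactivation leads to interruption of study drug until resolution. Then: "If resolution occurs within ≤ 28 days, study drug should be re-started at one dose lower". A patient already on the lowest dose restarts at that dose. For slower resolution the table says: "If resolution occurs > 28 days, patients should discontinue study drug". Its footnote records every reactivation as grade 3, "unless considered life threatening by the investigator, in which case they should be recorded as grade 4".

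**The general rules.**
- Section 6.1.4, the parent of 6.1.4.4: "If a patient requires a dose delay of >21 days from the intended day of the next scheduled dose, then the patient must be discontinued". Section 6.6.3.1 repeats this rule.
- Section 6.6.5: "If treatment has to be interrupted for more than 21 days due to suspected study drug-related toxicity, the patient will be discontinued from the study". The sentence before it sets a limit of more than 14 days for interruptions not suspected to be drug-related.
- Table 3 (Section 6.1.3), last row: "Any hematological or non-hematological toxicity" "requiring interruption for ≥ 3 weeks" leads to discontinuation of RAD001. Its row for grade 4 non-hematological toxicity also discontinues.
- Table 3, row for reactivation of HBV or HCV: "Please refer to Tables 6 and 7".

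SAP Section 3.2 points back to protocol Tables 2 to 4 for the interruption rules and sets no limit of its own.

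**The concern.** A stopping rule for safety gives two answers for one patient. Someone whose reactivation resolves in the fourth week of the hold is to be restarted under Table 6 and taken off under three other sections. The decision is whether to re-expose a patient after an event that is always recorded as grade 3 or 4. All patients are screened for HBV, and the text is to be applied at 25 sites in 11 countries, so different readings at different sites are a realistic prospect. An investigator in this position cannot comply with both rules, and Section 12 allows no authorized deviations. Treatment duration and reasons for discontinuation, both of which the SAP tabulates, would then partly reflect which paragraph a site happened to follow.

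**Working it through.** No sample size, power or error rate enters this point. The check is a day-by-day comparison of the rules.

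**Inputs.** Table 6: restart if resolved by day 28, otherwise stop. Sections 6.1.4, 6.6.3.1 and 6.6.5 (drug-related): stop if more than 21 days. Section 6.6.5 (other reasons): stop if more than 14 days. Table 3, last row: stop if 3 weeks or more, that is, 21 days or more.

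**Assumption.** The hold lasts until resolution, is counted in whole days from the first missed dose, and Table 6's clock starts on that same day.

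| Rule compared with Table 6 | Days on which Table 6 restarts and the other rule stops | Length |
|---|---|---|
| 6.1.4, 6.6.3.1, 6.6.5 drug-related (>21) | 22 to 28 | 28 − 21 = 7 days |
| 6.6.5, not drug-related (>14) | 15 to 28 | 28 − 14 = 14 days |
| Table 3, last row (≥21), if it applies to HBV | 21 to 28 | 28 − 20 = 8 days |

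Up to day 14 no rules conflict. After day 28 all of them stop treatment. On day 21 Table 3 stops and the sections with a limit of more than 21 days do not, so the general rules also disagree among themselves.

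**Dependence on the starting date.** Table 6 does not say what its 28 days run from. Its footnote dates a reactivation to the day the DNA (and ALT) criteria were met, while Section 6.1.4 counts from the next intended dose. Suppose the 28 days run from the reactivation date and the hold starts k days later, once results are known. The longest hold that Table 6 would still restart is then 28 − k days. The overlap with the 21-day rule is 7 − k days, and with the 14-day rule 14 − k days (zero if negative). For k = 0, 3 and 7 this gives 7, 4 and 0 days, and 14, 11 and 7 days.

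**Can the window be reached?** Resolution requires HBV-DNA at or below baseline. Scheduled HBV-DNA checks are every 3 or 6 weeks (Table 5) or every 28-day cycle (Table 9 footnote), so documented resolution could fall on day 21 or day 28. The weekly follow-up in Section 6.1.4 may detect it sooner.

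**How many patients?** The documents give no HBV prevalence, reactivation rate or time to resolution. Purely as an illustration, assume 5% to 20% of 110 patients are HBV-exposed, 20% of those reactivate, and 25% of reactivations resolve in the window:
- 110 × 0.05 × 0.20 × 0.25 ≈ 0.3 patients
- 110 × 0.20 × 0.20 × 0.25 = 1.1 patients

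**The case against.** **The specific rule prevails.** Table 3 gives reactivation its own row and sends it to the hepatitis tables, which can be read as taking it out of the rest of Table 3. The HCV table supports that reading: HCV reactivation, recorded as grade 3 by default, means stopping the drug, whereas Table 3's general grade 3 row interrupts and reintroduces. This stands as far as Table 3 goes. A reader might infer that every reactivation recorded as grade 4, and every hold of exactly 21 days, directly contradicts Table 6. The documents do not support this firmly, because both inferences require setting the referral row aside. What can be said is that Table 3 leaves it unstated whether its last row and its grade 4 row still apply.

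The referral does not reach Sections 6.1.4, 6.6.3.1 or 6.6.5, which contain no exception. Section 6.1.4 heads the very section that holds Table 6, and its limit is worded as an obligation. The pointer is also hard to follow: the hepatitis C table is captioned Table 6 as well, and the table captioned Table 7 is the Karnofsky scale.

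**Few patients are touched.** This stands. A reader might take 5% to 20% of 110, about 6 to 22 patients, as the number affected. That range counts assumed HBV exposure. Only patients who reactivate and also resolve inside the window meet the conflict. Exclusion criterion 12 may reduce the pool further.

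**The primary endpoint is not threatened.** This also stands. A reader might infer a bias in PFS through censoring at new anticancer therapy. Under Section 10.4.1, PFS is censored at the last tumor assessment before new therapy. Discontinued patients continue 12-weekly tumor assessments until such therapy begins, and the study is single-arm with no hypothesis test.

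**Investigators may act on safety.** Section 11.6 expects immediate action for safety even where it deviates from the protocol. That softens the Section 12 argument but does not tell a site which limit is the protocol's.

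**Conclusion.** The contradiction is in the current text and does not depend on Table 3. For holds of 22 to 28 days, or 15 to 28 days if the reactivation is judged not drug-related, Table 6 directs a restart while Sections 6.1.4, 6.6.3.1 and 6.6.5 direct discontinuation. Sites could handle the same patient in opposite ways within that window. Outside it they would not.

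The 7-day and 14-day widths assume that Table 6's clock starts with the first missed dose; they shrink if it starts earlier. Two secondary points remain: the boundary is written in two forms (at least 3 weeks, more than 21 days), and Table 3 is silent on whether its last row and grade 4 row apply to HBV reactivation. The number of patients affected cannot be derived from the documents and is probably small, and no material effect on PFS is shown. The reasons to act are patient safety and uniform handling across sites.

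**What to change.** Reconcile Table 6, Table 3 and Sections 6.1.4, 6.6.3.1 and 6.6.5 so that a single maximum hold governs HBV reactivation. This can be done by an explicit exception in the general rules or by aligning the limits. In the same amendment:
- use one form of the boundary throughout;
- state the day from which the hold is counted;
- say whether the 14-day limit in Section 6.6.5 can apply to a reactivation judged not drug-related;
- say whether a reactivation recorded as grade 4 follows Table 3 or Table 6;
- correct the table numbers in Table 3's referral row.

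The sponsor's medical team must choose the rule; no view is offered here on which limit is right. The cost is a text amendment with its approvals, and no added visits, tests or patients. If treatment has already ended, the study report should state which rule was applied to each patient whose hold fell in the window.

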6.1.5 How Supplied

6.1.5.1 Study Drug

RAD001 will be provided by Novartis at no charge to the study site. RAD001 is formulated as tablets of 5 mg strength for oral administration. Tablets should be opened only at the time of administration, as the drug is both hygroscopic and light sensitive.

Medication labels will comply with the legal requirements of each country and are printed in the local language. The labels do not contain information about the patient. The storage conditions for the study drug will be described on the study drug label.

Each study site will receive the study drug (RAD001). After a final drug accountability/reconciliation review has been performed by the study monitor, unused, used, and empty study drug packaging and any unused tablets will be destroyed at the end of the study according to local regulatory procedures. All local regulatory procedures must be followed.

6.1.6 Preparation and Storage

6.1.6.1 Study Drug

RAD001 is supplied as 5 mg tablets. Patients will be supplied with enough tablets for a complete 28-day cycle. Tablets should be stored in a secure, dry, light-proof medicine cabinet.

6.2 Treatment Arms

One treatment arm: RAD001.

6.3 Patient Numbering

Patient informed consent must be obtained before any screening testing is performed to determine the patient's eligibility. At screening (Visit 1), upon signing the informed consent form, the patient is assigned a unique patient number by the investigator or his/her designee.

The patient number is a 9-digit number. The first part is the site number (first 4 digits) and the second part (last 5 digits) is one of a series of numbers allocated to patients at that site. The site number is assigned by Novartis. The patient identification numbers will be assigned in a sequential manner. Once assigned, the patient identification number will not be reused. At screening (Visit 1), the investigator or his/her designee will record the patient identification number appropriately on the CRFs.

6.4 Treatment Assignment

This is a single arm study with one dose of study drug. All patients will initiate treatment with 10 mg/day RAD001.

6.5 Treatment Blinding

This is an open-label study.

6.6 Treating the Patient

6.6.1 Commencing Treatment

At Visit 1 (Screening, Visit 1a) and Visit 2 (Baseline, Visit 1b), the investigator or his/her designee will verify that the patient fulfills all the inclusion/exclusion criteria to commence RAD001 treatment. The Baseline Visit should be no sooner than 28 days and no later than 35 days after the Screening Visit. Study treatment can commence (Visit 2) immediately after the Baseline Visit.

Patient stratification will be based on previous cytokine therapy.

6.6.2 Study Drug Administration

The study drug will be self-administered (by the patients themselves). The investigator will instruct the patient to take the study drug exactly as specified in the protocol.

Patients will be instructed to take RAD001 (two 5 mg tablets at once, ie., one tablet after another) orally daily with a glass of water, at the same time each day in a fasting state or with a light fat-free meal.

If vomiting occurs, no attempt should be made to replace the vomited dose. Any dietary habits around the time of RAD001 intake should be as consistent as possible throughout the study.

RAD001 will be taken daily from Visit 2 (Day 1) until disease progression, unacceptable toxicity, death, or discontinuation from the study for any other reason.

6.6.3 Permitted Study Drug Adjustments

Dose adjustments are permitted in those patients who are unable to tolerate the protocol-specified dosing schedule. If administration of RAD001 must be interrupted because of unacceptable toxicity, drug dosing will be interrupted or modified according to the rules described in Section 6.1.3.

6.6.3.1 Follow-Up for Toxicities

Patients whose treatment is interrupted or permanently discontinued due to an AE or abnormal laboratory value suspected to be related to RAD001 must be followed at least weekly until the AE or abnormal laboratory value resolves or returns to grade 1.

If a patient requires a dose delay of >21 days from the intended day of the next scheduled dose, then the patient must be discontinued from the study.

6.6.4 Concomitant Medications

Patients will be instructed not to take any additional medications (including over-the-counter products) during the course of the study without prior consultation with the investigator.

At each visit, the investigator will ask the patient about any new medications he/she is or has taken after the start of the study drug. All medications taken ≤ 30 days prior to study entry should be recorded on the Concomitant Medications/Significant Non-Drug Therapies Prior to Start of Study Drug CRF page. All medications (other than the study drug) and significant non-drug therapies (including physical therapy and blood transfusions) administered after the patient starts treatment with study drug must be listed on the Concomitant Medications/Significant Non-Drug Therapies CRF. Prior and concomitant medications will be coded to indication-specific Anatomic Therapeutic Chemical classification (ATC) and preferred name using the World Health Organization (WHO) Drug Dictionary (latest version).

Permitted treatments during the study include:

- Bisphosphonate therapy for treatment of bone metastases. This therapy should be initiated before the patient is enrolled into the study;
- Pain medication to allow the patient to be as comfortable as possible;
- Localized radiotherapy, for the treatment of pre-existing, painful bone metastases is allowed during the study only if evidence of radiological progression is not present. Radiotherapy for brain metastases is not permitted during the course of the study (the need for CNS radiation will constitute disease progression);

- Nutritional support as recommended by the investigator;
- Megesterol acetate may be prescribed during the course of the study as an appetite stimulant;
- Oxygen therapy and blood transfusions.

The following restrictions apply during the entire duration of the study:

- No other investigational therapy should be given to patients;
- No anticancer agents other than the study drug (RAD001) should be given to patients. If such agents are required for a patient, then the patient must first be withdrawn from the study;
- Leukocyte growth factors (e.g., colony-stimulating factor and granulocyte-macrophage colony-stimulating factor) are not to be administered prophylactically, but may be prescribed by the investigator for severe neutropenia if this is thought to be appropriate;

Drugs or substances known to be inhibitors or inducers or substrates of the isoenzyme CYP3A4 should be avoided in association with RAD001 because these can alter the metabolism of RAD001. In addition, patients should refrain from grapefruit juice, which is a potent CYP3A4-inhibitor. Complete details are provided in Table 8.

Table 8 Clinically Relevant Drug Interaction: Substrates, Inducers, and Inhibitors of Isoenzyme CYP3A

Substrates (competitive inhibition)	
Antibiotics ^a :	Calcium channel blockers:
clarithromycin*	amlodipine
erythromycin	diltiazem
telithromycin*	felodipine
Anti-arrhythmics:	nifedipine
quinidine	nisoldipine
Benzodiazepines:	nitrendipine
alprazolam	verapamil
diazepam	HMG -CoA reductase inhibitors ^b :
midazolam	cerivastatin
triazolam	lovastatin
Human immunodeficiency virus protease inhibitors:	simvastin
indinavir*	Miscellaneous:
ritonavir*	aprepitant
saquinavir*	bupirone
Prokinetic:	haloperidol
cisapride	methadone
Antihistamines:	pimozide
astemizole	quinine
chlorpheniramine	sildenafil
	tamoxifen
	trazodone
	vincristine
Inducers	

Carbamazepine	Rifampin*
Phenobarbital	St. John's wort
Phenytoin*	Troglitazone
Rifabutin*	
Inhibitors	
Amiodarone	Indinavir
Cimetidine	Itraconazole*
Clarithromycin	Ketoconazole*
Delaviridine	Voriconazole*
Diltiazem	Posaconazole*
Erythromycin	Mibefradil
Fluvoxamine*	Nefazodone*
Grapefruit juice	Nelfinavir*
Sevilla orange	Troleandomycin
	Verapamil

Base on: Ingelman-Sundberg M. Human drug metabolising cytochrome P450 enzymes: Properties and polymorphisms. Naunyn Schmiedebergs Arch Pharmacol 2004;369:89-104 (<http://www.medicines.iupui.edu/flockhart/clinlist.htm>).

* Denotes strong inhibition/induction. Please note:

- Strong inhibitor implies that it can cause ≥ 5 -fold increase in area under the concentration curve (AUC) or $\geq 80\%$ decrease in clearance of sensitive CYP substrates;
- Moderate inhibitor implies that it can cause 2 to 5-fold increase in AUC values or 50% to 80% decrease in clearance of sensitive CYP substrates.

(Distinction is not always categorical as interaction can vary depending on conditions).

^a Macrolide antibiotics: Azithromycin is not a CYP3A substrate. It may therefore be employed where antibiotic therapy with a macrolide is desirable in a patient being treated with RAD001.

^b Statins: Pravastatin may be taken with RAD001 since a pharmacokinetic interaction study has shown that there is no relevant pharmacokinetic interaction.

